3.1.2 Network Members

Individuals must meet all of the following criteria to be eligible for inclusion in the study as a **network member:**

- Of legal age to independently provide written informed consent for research
- Recruited for the study by an eligible index participant
- Have injected drugs with and/or had sex with the relevant index participant within the three months prior to screening
- Provide written informed consent for study participation

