3.1 Inclusion Criteria

3.1.1 Index Participants

Individuals must meet all of the following criteria to be eligible for inclusion in the study as an **index participant:**

- Of legal age to independently provide written informed consent for research
- Provide written informed consent for screening and study participation
- Report having injected drugs at least 12 times in the last three months
- Been out of methadone maintenance treatment for at least 3 months and have relapsed
- HIV negative on specimen obtained within 60 days prior to randomization
- Willing to identify and attempt to recruit at least two HIV risk network members who are eligible for study participation according to the criteria in Sections 3.1.2 and 3.2.2.
- Able to recruit at least one HIV risk network member who is eligible for study participation according to the criteria in Sections 3.1.2 and 3.2.2.

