3.3 Recruitment Setting

Study participants will be recruited from the following HPTN sites:

Philadelphia, Pennsylvania, USA

IDUs in Philadelphia will be recruited from neighborhoods with high concentrations of drug use, drug sales, and diagnosed AIDS cases. Guided by an established network of community gatekeepers, field staff will identify prospective index participants using van-based street outreach. Volunteers will be scheduled for a screening visit at one of two office-based locations, either the West Philadelphia research offices of the Treatment Research Center or the North

Philadelphia field site. It is anticipated that for this study, approximately 28 participants (ten index participants and 18 network members) per month will be entered into the study at these sites during the 30-month enrollment phase.

These recruitment strategies were utilized in a prospective vaccine preparedness cohort study (VPS II) and a New HIVNET IDU Study conducted in Philadelphia. The primary objectives of the VPS II were to examine the incidence of HIV infection among women at heterosexual risk and to expand the number of injectors at high risk. Recruitment began in July 1999 and over 6 months 222 HIV-uninfected IDUs were enrolled. After six months of follow-up, participants had a 94% retention rate and an incidence of HIV infection of 3.8 per 100 person years. At the close of the study (12 months of follow-up), HIV incidence was 2.04 per 100 person years and retention, 93%. Recruitment for the HIVNET NEW IDU Study began in August 1997 and over 10 months 262 HIV-uninfected injection drug users at high-risk of HIV infection, defined as not in methadone treatment and not using needle exchange, were enrolled. Follow-up was for 15 months. To be eligible, injectors had to have visible signs of recent injection and report injecting at least three days per week during the prior three months. Recruitment and follow-up were conducted from the study's mobile assessment unit and from drug detoxification programs. At 6 months there was a 93% retention rate and an HIV incidence rate of 2.5 per 100 person years. After 15 months, the retention rate was 88% and the incidence of HIV infection was 1.8 per 100 person years at risk.

Chiang Mai and Chiang Rai, Thailand

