IDUs in Thailand will be recruited using street outreach in the cities of Chiang Mai and Chiang Rai, Thailand and from the Northern Drug Dependence Treatment Center (NDTC), which is located about 15 kilometers north of Chiang Mai and Chiang Rai and services both cities. This center is an inpatient facility operated by the Department of Medical Services, Ministry of Public Health. Patients are admitted for a maximum stay of 21 days; approximately 25% of patients leave against medical advice. It is estimated that the relapse rate among injection drug users is 90% within one year and based on re-admission data is over 50% within the first three months following discharge (personal communication [name], NDTC Director). It is anticipated that approximately 59 participants (20 index and 39 network members) per month will be entered into the study at these sites during the 30-month enrollment phase.

The NIDA HIV Prevalence Study (*1 R01 DA11133-01A1*) enrolled 1,865 substance users from the Northern Drug Dependence Treatment Center. The prevalence of HIV infection among the 879 injection drug using participants in the NIDA study was 35.2% with the use of injection drugs associated with HIV infection. As of December 2002, in the ongoing, two-year, follow-up incidence phase of the same NIDA-funded study retention is 97%. HIV incidence in the cohort is 7.89 per 100 person-years among the IDU in follow-up. Only individuals who have been out of treatment for at least three months and have relapsed will be recruited for participation as index participants.

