7.2.2 Secondary Endpoints– Self reported HIV Risk Behaviors

Self- reported HIV risk behaviors for indexes and network members, as follows:

- Frequency of injection drug use
- Frequency of sharing of injection equipment (needles, cookers, cotton, and rinse water)
- Number of people injection equipment shared with
- Frequency of properly disinfecting injection equipment
- Entering into drug treatment
- Cessation of injection drug use
- Number of sex partners
- Frequency of condom use during sex

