7.3.1 Power for seroincidence endpoints

Philadelphia has established a seroincidence rate of 2 per 100 person-years and the current rate established in Thailand among IDU is 10.4 per 100 person-years, although in the sample size computations a conservative 8% rate is used. One-third of the networks will enroll in Philadelphia and two-thirds in Thailand.

Sample size computations are made using the following assumptions:

- Mean seroincidence rate: 6% per year for pooled sites, 8% per year for the Thai sites.
- Loss to follow up 10% per year
- 30 months recruitment, minimum 18 months follow up, maximum 30 months
- 90% power, 5% Type I error

The formula above is used, substituting for P_E and P_C estimates \overline{P}_E and \overline{P}_C , the average probability of seroconverting during the study on the experimental and control arms. These estimates take loss to follow-up and differential length of follow-up into account.

Rate	Effect	\overline{P}_{F}	\overline{P}_{c}	K	Total/	Networks/	Total/	Networks/	Total/	Networks/
		L	C		arm	arm	arm	arm	arm	arm
					Mean pe	er network $= 4$	Mean pe	er network $= 3$	Mean pe	er network $= 2.5$
6%	33%	7.8%	11.6%	0.1	1671	418	1542	515	1478	592
				0.2	2057	515	1800	600	1671	669
				0.3	2442	611	2057	686	1864	746
6%	40%	7.1%	11.6%	0.1	1112	278	1026	343	983	394
				0.2	1368	343	1197	400	1112	445
				0.3	1625	407	1368	457	1240	496
8%	33%	10.4%	15.3%	0.1	1246	312	1150	384	1102	441
				0.2	1534	384	1342	448	1246	499
				0.3	1821	456	1534	512	1390	556
8%	40%	9.4%	15.3%	0.1	828	208	765	255	733	294
				0.2	1020	255	892	298	828	332
				0.3	1211	303	1020	340	924	370

 Table 1: Sample size requirements for two-arm group randomized network study

The sample size has been chosen to achieve 90% power to detect a 40% reduction in rate of infection, from 6% per year to 3.6% per year. This requires 445 networks per arm, followed for an average of 27 months (minimum of 18 month, maximum of 30 months), with a seroincidence evaluation of an average of 2.5 HIV-uninfected people per network (HIV-uninfected peer leader and one or more network members, HIV-uninfected at enrollment) and loss to follow-up of 10% per year, using two-sided alpha of 0.05 and intraclass correlation of 0.2. To achieve the same power to detect a 33% reduction, from 6% to 4%, requires 669 networks per arm.

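### Injection endpoints are compared in all indexes and members, although a member may qualify through sex alone: this dilutes the arm difference and mixes role with injecting status

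*Protocol*

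**What the plan says.** **Eligibility.** Protocol section 3.1.1 requires of an index: "Report having injected drugs at least 12 times in the last three months". Every index is therefore an injector. For a network member, section 3.1.2 asks: "Have injected drugs with and/or had sex with the relevant index participant within the three months prior to screening". Section 3.2.2 does not exclude non-injectors.

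**Behavioral endpoints.** Section 7.2.2 lists self-reported behaviors for indexes and network members together. Among them are injection frequency, "Frequency of sharing of injection equipment (needles, cookers, cotton, and rinse water"), disinfection and cessation of injecting. Section 7.5.2 compares arms in network aggregates (item 1), in indexes alone (item 2) and between indexes and networks (item 3). Item 3 serves secondary objective 3. Section 7.2.3 builds network norms by aggregating the same reports within networks.

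**Role of these endpoints.** Section 7.3.2 says the primary outcome cannot show the effect in Philadelphia, so self-reported behavior will be used there. Table 2 gives networks per arm for network aggregates.

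**Planning rates.** Section 7.3.1 states "Philadelphia has established a seroincidence rate of 2 per 100 person-years". For Thailand it cites 10.4 per 100 person-years among injection drug users, "although in the sample size computations a conservative 8% rate is used". Section 3.3 gives for Thailand "HIV incidence in the cohort is 7.89 per 100 person-years among the IDU in follow-up". The pooled 6% is applied to all 2.5 HIV-uninfected people per network.

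**The concern.** A sex partner who does not inject reports no injecting and no sharing in either arm. Disinfection frequency has no denominator for that person, and cessation is undefined or fixed by coding. Such a person adds to the denominator of these endpoints but cannot carry an effect.

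Two comparisons suffer. The network-aggregate difference between arms shrinks, at the site where behavior is the evidence of effect. And because all indexes inject while some members may not, a weaker effect in members can arise from the mix of injectors even if the intervention works equally well in every injector. Secondary objective 3 would then be answered wrongly.

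A lesser question concerns the primary endpoint. Rates observed in injectors are applied to everyone, with no allowance for sex-only members.

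**Working it through.** **1. Reproduce Table 2** (40% vs 50%, kappa 0.2, cluster size 12). The section 7.3 formula, as networks per arm, is

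(z_α + z_β)² × [P_E(1−P_E) + P_C(1−P_C)] × [1 + (n−1)κ] / [(P_E−P_C)² × n]

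The variance term is 0.24 + 0.25 = 0.49 and the design effect is 1 + 11 × 0.2 = 3.2. The result is 102.6 networks at 80% power and 137.3 at 90%; the protocol has 103 and 138.

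**2. Dilute it.** Let f be the share of members who do not inject (assumed; the protocol gives none). With 1.9 members among 2.9 people per network, both prevalences are multiplied by w = 1 − f × 1.9/2.9. This reads Table 2's prevalences as holding among injectors. Power at 150 networks per arm is Φ(difference/SE − 1.96), with SE² = [P_E(1−P_E) + P_C(1−P_C)] × 3.2/(150 × 12).

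| f | w | P_E vs P_C | Difference (points) | Power |
|---|---|---|---|---|
| 0 | 1.000 | 40.0% vs 50.0% | 10.0 | 92% |
| 10% | 0.934 | 37.4% vs 46.7% | 9.3 | 89% |
| 25% | 0.836 | 33.4% vs 41.8% | 8.4 | 83% |
| 40% | 0.738 | 29.5% vs 36.9% | 7.4 | 75% |

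**3. Restrict to injectors instead.** The difference stays at 40% vs 50%, and the cluster shrinks to n = 12w: 11.2, 10.0 and 8.9 reports per network. The same formula gives power of 92%, 91% and 90% at f = 10%, 25% and 40%. The smaller denominator costs much less than the dilution.

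**4. Index-versus-member contrast.** Suppose the effect is 50% to 40% in every injector. Indexes show 10 points. Members show 10 × (1 − f), which is 7.5 points at f = 25%, a gap of 2.5 points due to the mix alone. On the odds-ratio scale, indexes show (0.40/0.60)/(0.50/0.50) = 0.67. Members show (0.30/0.70)/(0.375/0.625) = 0.71. A ratio of proportions stays at 0.80, so there only precision is lost.

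**5. Primary endpoint.** First the plan's own figure. The pooled rate is 1/3 × 2% + 2/3 × 8% = 6%. Take P = h/(h+m) × (1 − exp(−(h+m)t)), with t = 27 months = 2.25 years, h = −ln(1 − rate) and m = −ln(0.9). This gives P_C = 11.60%, P_E = 7.06% and 445.6 networks per arm, against 445 stated.

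Now let s be the sex-only share of the 1.5 uninfected members and r their incidence relative to injectors (both assumed). Members are 1.5/2.5 = 60% of the primary population, so the pooled rate becomes base × [1 − 0.6 × s × (1 − r)]. The 40% effect is held constant. Power at 445 networks per arm:

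| Thai rate | Undiluted | s = 25%, r = 0.5 to 0.25 | s = 40%, r = 0.5 to 0.25 |
|---|---|---|---|
| 8% (used) | 90% | 88% to 86% | 86% to 83% |
| 7.89 per 100 person-years (section 3.3) | 90% | 87% to 86% | 85% to 83% |
| 10.4 per 100 person-years (section 7.3.1) | 95.5% | 94% to 93% | 93% to 91% |

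For example, at 8% with s = 25% and r = 0.25, the pooled rate is 6% × (1 − 0.6 × 0.25 × 0.75) = 5.33%.

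**The case against.** Table 2 is labelled for network aggregates, uses generic prevalences, and does not say that 40% vs 50% holds among injectors. If those figures already describe mixed networks, the table is right as it stands. That is correct, so the power losses in step 2 depend on a reading. The structural zeros and the index-versus-member problem do not.

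Philadelphia also has an index-only analysis, which contains no sex-only member. That stands as well. But Table 3 powers it mainly for 15-point changes, and it cannot show whether the effect reached members.

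Denominators for single items are often left to the analysis plan, and section 7.5.2 will consider covariates for drug type, injection frequency and network characteristics. Here, however, the protocol itself fixes the population as indexes and members, and covariate adjustment does not give a non-injector the scope to change. The argument against restricting the network-norm aggregates of section 7.2.3 is sound: that would change what they measure.

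Two stronger readings are tempting.

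- A reader might infer that the stated primary power describes another population. The documents do not support this. All indexes inject, members may inject, the sex-only share is unknown, and 445 networks and 6% both reproduce. Section 7.3.1 calls 8% conservative against 10.4, and section 7.3.4 promises close monitoring of seroincidence. If sex-only members have lower HIV prevalence than the injector figures assumed, more of them count for the primary endpoint, which is a partial offset. Against this, the 7.89 in section 3.3 puts the cushion in doubt, and the explicit adjustment rule in section 7.6 concerns only the number of HIV-uninfected members.
- A reader might infer that the Philadelphia rate is inflated by heavier injectors, since in one source cohort "injectors had to have visible signs of recent injection and report injecting at least three days per week during the prior three months". That cohort ended with the lower incidence, 1.8 per 100 person-years. In the other, for which no frequency rule is given, "HIV incidence was 2.04 per 100 person years and retention, 93"%, and the planned 2 lies nearest to it. Halving the Philadelphia rate would cost only about 2 points of primary power.

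**Conclusion.** The point holds for the injection endpoints. The protocol admits members who need not inject and then compares injecting behavior in everyone. This dilutes the arm difference in network aggregates and, on the difference or odds-ratio scale, biases the contrast between indexes and members. For Philadelphia, power falls from 92% to about 89%, 83% and 75% at assumed non-injecting shares of 10%, 25% and 40% of members. This applies at kappa 0.2, with Table 2's 40% vs 50% read as prevalence among injectors.

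For the primary endpoint the point is secondary. With 25% to 40% sex-only members at 25% to 50% of injector incidence, power is about 83% to 88% rather than 90% at a Thai rate of 8%. It stays above 90% if the Thai rate is 10.4 per 100 person-years. The arithmetic of section 7.3.1 is sound; the missing elements are a label on the rates and a range. All shares and relative rates here are assumptions.

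**What to change.** 1. In sections 7.2.2 and 7.5.2, make the main comparison of the injection endpoints (frequency, sharing, disinfection, cessation), including the index-versus-member contrast, in participants who reported injecting at screening. Analyse sexual endpoints in all participants. Keep the all-participant analysis of injection endpoints as supportive, and leave the network-norm aggregates of section 7.2.3 on the full network.
2. In section 7.3.1, label the 2% and 8% as injector rates, reconcile 10.4 with the 7.89 per 100 person-years in section 3.3, and show primary power over a stated range of sex-only members and their relative incidence.

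Eligibility need not change. The cost is wording: the eligibility and baseline risk surveys already precede randomization. The downsides are a smaller denominator for injection endpoints, and that non-injectors who start injecting appear only in the supportive analysis.

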3.2 Exclusion Criteria

3.2.1 Index Members

Individuals who meet any of the following criteria will be excluded from the study as an **index participant:**

- Prior or concurrent enrollment in the last 6 months in another HIV behavioral or biomedical prevention study (HIV vaccine research, HIV microbicide research, or any other behavioral or clinical research to test an intervention aimed at preventing or reducing the risk of HIV infection)
- Appearance of psychological disturbance or cognitive impairment that would limit the ability to understand study procedures, as determined by clinic staff
- Any other condition that, in the opinion of the investigator, would make participation in the study unsafe, or otherwise interfere with the study objectives
- Enrollment as a network member or index participant in another network of HPTN 037

3.2.2 Network Members

Individuals who meet any of the following criteria will be excluded from the study as **network members:**

- Appearance of psychological disturbance or cognitive impairment that would limit the ability to understand study procedures, as determined by clinic staff
- Any other condition that, in the opinion of the investigator, would make participation in the study unsafe, or otherwise interfere with the study objectives
- Enrollment as a network member or index participant in another network of HPTN037

3.3 Recruitment Setting

Study participants will be recruited from the following HPTN sites:

Philadelphia, Pennsylvania, USA

IDUs in Philadelphia will be recruited from neighborhoods with high concentrations of drug use, drug sales, and diagnosed AIDS cases. Guided by an established network of community gatekeepers, field staff will identify prospective index participants using van-based street outreach. Volunteers will be scheduled for a screening visit at one of two office-based locations, either the West Philadelphia research offices of the Treatment Research Center or the North

Philadelphia field site. It is anticipated that for this study, approximately 28 participants (ten index participants and 18 network members) per month will be entered into the study at these sites during the 30-month enrollment phase.

These recruitment strategies were utilized in a prospective vaccine preparedness cohort study (VPS II) and a New HIVNET IDU Study conducted in Philadelphia. The primary objectives of the VPS II were to examine the incidence of HIV infection among women at heterosexual risk and to expand the number of injectors at high risk. Recruitment began in July 1999 and over 6 months 222 HIV-uninfected IDUs were enrolled. After six months of follow-up, participants had a 94% retention rate and an incidence of HIV infection of 3.8 per 100 person years. At the close of the study (12 months of follow-up), HIV incidence was 2.04 per 100 person years and retention, 93%. Recruitment for the HIVNET NEW IDU Study began in August 1997 and over 10 months 262 HIV-uninfected injection drug users at high-risk of HIV infection, defined as not in methadone treatment and not using needle exchange, were enrolled. Follow-up was for 15 months. To be eligible, injectors had to have visible signs of recent injection and report injecting at least three days per week during the prior three months. Recruitment and follow-up were conducted from the study's mobile assessment unit and from drug detoxification programs. At 6 months there was a 93% retention rate and an HIV incidence rate of 2.5 per 100 person years. After 15 months, the retention rate was 88% and the incidence of HIV infection was 1.8 per 100 person years at risk.

Chiang Mai and Chiang Rai, Thailand

IDUs in Thailand will be recruited using street outreach in the cities of Chiang Mai and Chiang Rai, Thailand and from the Northern Drug Dependence Treatment Center (NDTC), which is located about 15 kilometers north of Chiang Mai and Chiang Rai and services both cities. This center is an inpatient facility operated by the Department of Medical Services, Ministry of Public Health. Patients are admitted for a maximum stay of 21 days; approximately 25% of patients leave against medical advice. It is estimated that the relapse rate among injection drug users is 90% within one year and based on re-admission data is over 50% within the first three months following discharge (personal communication [name], NDTC Director). It is anticipated that approximately 59 participants (20 index and 39 network members) per month will be entered into the study at these sites during the 30-month enrollment phase.

The NIDA HIV Prevalence Study (*1 R01 DA11133-01A1*) enrolled 1,865 substance users from the Northern Drug Dependence Treatment Center. The prevalence of HIV infection among the 879 injection drug using participants in the NIDA study was 35.2% with the use of injection drugs associated with HIV infection. As of December 2002, in the ongoing, two-year, follow-up incidence phase of the same NIDA-funded study retention is 97%. HIV incidence in the cohort is 7.89 per 100 person-years among the IDU in follow-up. Only individuals who have been out of treatment for at least three months and have relapsed will be recruited for participation as index participants.

3.4 Recruitment Process

Approximately 600 networks will be enrolled in Chiang Mai and Chiang Rai, Thailand, and approximately 300 networks will be enrolled in Philadelphia, Pennsylvania, USA. Each network will consist of an HIV-uninfected index participant and an average of 1.5 HIV-uninfected and 0.4 HIV-infected network members. Therefore, approximately 2,610 participants will be enrolled in

the study during a 30-month enrollment period. (See the study design and randomization schema on page 3.)

Screening of each index and his/her network members will take place over a period of up to 60 days. This study will largely employ a street outreach-based approach to participant recruitment. Prospective index participants will be first identified by targeting specific geographic areas, that is, outreach will be conducted in areas in the cities of high drug use. The outreach workers will also identify other settings or organizations frequented by drug users. In these geographic areas and settings outreach workers will disseminate information about the study, provide verbal and written descriptions of the studies to prospective participants, and will encourage prospective index participants to participate in screening activities at a local study site. Prospective participants will also be informed that, if the study does not apply to them, they should pass the information on to other individuals.

Outreach workers will be trained to not pre-select individuals who fit their description of "drug users," rather they will provide information to a range of individuals and encourage those individuals to pass information about the study to others in the community. Outreach workers will be selected from the community and must be knowledgeable about the community's dynamics and trained on basic methods of rapid assessment procedures in order to target areas of high drug use. They will also be trained, as part of the study, in methods of approaching and communicating with potential participants, personal safety, and confidentiality.

Prospective index participants who present at the study site will be offered HIV counseling and testing and receive a brief introduction to the study. Indexes that are interested in participating will be asked to provide written informed consent for screening. A sample of the consent form can be found in Appendix III. After providing informed consent for screening, volunteers will undergo an eligibility screening survey. If at any time during screening, they are found to be ineligible, screening will be discontinued; however, HIV counseling and testing will be offered to all persons who present for screening. The survey will include questions about recent injection drug use and the size and structure of their risk networks. Participants who meet initial study screening eligibility criteria will be administered a baseline risk behavior survey and then undergo enhanced risk reduction counseling and HIV testing. Participants will be scheduled for a visit to return for their HIV test result and post-test counseling either the same day (for rapid testing) or in approximately one week (for standard testing). HIV-uninfected, prospective, index participants are eligible for enrollment and will be offered further screening and asked to provide study consent. A sample of the consent form can be found in Appendix IV. HIV-infected, screening participants are not eligible for enrollment as indexes but will be offered referrals to support services as described in Section 8.4.1.

After consenting for study participation, prospective index participants will be asked to supply the initials, ages, and brief physical descriptions of the people with whom they inject drugs and of their sexual partners. Participants will then be provided with individual cards marked with their identification number to facilitate the recruitment of their network members. There will be no identifying information on the cards to indicate participation is in a HIV or drug use study. The prospective index participants will be asked to give the cards to network members and to encourage each network member to bring his or her card with them to the local study site to serve as their identification for participation in screening. (Note: Index participants will only be able to recruit as network members those individuals they have identified at their screening.) Within 60 days of each prospective index participant's pre-test counseling session, their prospective

network members will be able to go to the local study site to participate in study screening, as described above.

For prospective network members to participate in the screening process they must either present at a local study site with a card bearing their prospective index participants' ID number, or match the description provided by the index during his or her screening survey in terms of age, gender, frequency of contact with the index, and duration of relationship with the index. Prospective network participants will then be asked to provide study informed consent. Individuals who provide study consent will complete the network member screening survey, the baseline risk behavior survey, and will participate in HIV risk reduction counseling and testing. All individuals who participated in pre-test counseling and testing must return for their HIV test results and post-test counseling for eligibility. Network participants will be able to enroll only once in the study. Once an individual is enrolled in the study as a "network member", he/she will be unable to enroll as an index, or in any other study network.

It is important to note that, throughout screening, the study staff will clearly explain and emphasize to participants that although they themselves may screen eligible for the study, the final decision regarding enrollment will depend on the other network members who are eligible for the study. This will be determined after all network members have been screened.

